7.0 STUDY PARAMETERS - Test Schedule for cycle 1-12

Cycle (C) = 28 days	Screening	Cycle 1			CTE Period Cycles 2-4	Cycle 5-12	End of Treatment ⁶
Procedure \ Days (D)	21-0	Day 1 ± 3days	Day 8	Day 28	Day 1 ⁷	Day 1	
Informed consent	Χ						
Pathology confirmation of diagnosis of DLBCL or transformed DLBCL.	X						
Medical history	X						
Physical examination ¹	Χ	X	Χ		Χ	X	
Vital signs (pulse rate, BP, temperature) ¹	X	X			X	X	
ECOG performance status ¹	Χ	Χ			Χ	X	
Optional lymph node biopsy ₈		Χ	Χ				X
Mandatory Research							
peripheral blood samples 9		Χ	Χ	Χ	X9	X ⁹	X
EKG	Χ						
Serology: HCV, HBV ²	Χ						
Umbralisib	Defined by (Grouping (A,B	,C)		Daily (1-28)	Daily (1-28)	
Ibrutinib	Defined by 0	Grouping (A,B	,C)		Daily (1-28)	Daily (1-28)	
Hematology ¹	X ⁷	X	Χ		X	X	
Serum Chemistry ¹	X ⁷	Χ	Χ		Χ	Χ	
Lactate dehydrogenase (LDH)	Χ		Χ		Χ	X	
Serum Pregnancy test ³	Χ						
Radiographic Tumor Evaluation ⁴	X				X ⁵	X ⁵	

¹ Physical Exam, Vital Signs, ECOG PS, Hematology and Serum Chemistry visit days have +/- 3 day window in cycle 1 and +/- 7 day window during cycles 2-12.

²To confirm negative HBV and HCV

³ For women of child bearing potential completed within 14 days prior to Day 1 of Cycle 1

⁴Tumor evaluation must include a PET/CT; if a Deauville 3 (CR) is achieved then CT chest, abdomen and pelvis with contrast may be used. Further PET/CT scans are optional at the investigators discretion. All tumor evaluations have +/- 7 day window.

⁵ Response evaluation will occur after cycle 2, 4, 6, 9, and 12 (+/- 7 days). After Month 12, efficacy assessments should occur at the investigators discretion.

⁶ End of study will be the next visit following a cycle after study drug was administered. If a patient has completed 12 cycles of treatment without evidence of PD the patient will be monitor for relapse or progression at the discretion of the treating investigator. Follow up after 1 year of therapy will be per institutional guidelines. Patient can be taken off study to proceed to allogeneic stem cell transplant. Patients will be censored for EFS and DOR, but will be available for OS assessment.

⁷ The study will be terminated if a cumulative toxicity event (CTE) occurs in: ≥2/first 4; ≥4/first 8; or if more than 12 patients when the last (24th) evaluable patients has completed cycle 4. If a patient has progression of disease or is removed from study not related to a CTE after completion of 2 cycles but less than 4 cycles the patient's safety evaluation will be included, but noted appropriately. If less than 2 cycles than the patient will not be included and noted, but will not be replaced. The stopping rule would be appropriately adjusted if this were to occur.

Page 28 of 65

⁸ Optional biopsies obtained via US or CT guided biopsy of accessible lymph node: Day 0 (pre-treatment; core biopsy), day 8 (fine needle aspiration) and end of treatment (progressive disease or end of study treatment—1 year; core biopsy). At the discretion of the treating investigator, patient on non-coumadin based anticoagulation should have anticoagulant held for biopsy.

⁹Mandatory research peripheral blood samples will be collected in a 20 ml EDTA tube pretreatment (day of biopsy or initiation of treatment; (+/- 3 days)), day 8 (+/- 3 days), 1 month (+/- 3 days) and 10 mL at subsequent radiographic response assessments, after cycle 2, 4, 6, 9, and 12. (+/- 7 days). After Month 12, efficacy assessments should occur at the investigators discretion with 10mL EDTA peripheral blood samples obtained ONLY IF FEASIBLE.]

Section 8.0 Drug Formulation and Procurement:

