5.1 Pre-treatment Evaluations Standard of Care (SOC)

Within 21 days prior to the Date of Enrollment, date of the start of study treatment / first study related intervention (unless otherwise specified below). No tests or procedures are conducted solely for the purposes of research to determine subject eligibility.

- History and physical
- Informed Consent
- CBC, diff, platelets, CMET, LDH
- Hepatitis B (HBV) or C (HCV) serology
- Serum pregnancy test (if applicable) within 14 days of first study-related treatment date.
- Height and weight
- Vital signs, including blood pressure
- Performance Status
- EKG
- PET/CT baseline radiologic evaluation; NOTE for f/u if a Deauville 3 (CR) is achieved then CT chest, abdomen and pelvis with contrast may be used. Further PET/CT scans are optional at the investigators discretion.
- Mandatory research peripheral blood (20 mL) for cell free DNA assessment and T-cell characterization will be collected in an EDTA tube pretreatment (day of biopsy or initiation of treatment), day 8, 1 month (+/- 3 days) and 10mL at subsequent radiographic response assessments, after cycle 2, 4, 6, 9, and 12. (+/- 7 days). After Month 12, efficacy assessments should occur at the investigators discretion with collection of a research blood sample only if feasible. Should the patient consent any leftover peripheral blood collected for research will be stored at UNMC for future IHC and DNA unspecified research use.
- Optional Research Samples (Appendix G):
 - Should the patient consent, 3 additional optional lymph node biopsies for molecular profiling will be obtained at days 0 (pre-treatment; core biopsy), day 8 (FNA) and end of treatment (progressive disease, toxicity, or end of study—1 year; core biopsy) to evaluate the baseline characteristics and dynamic shifts in mutational landscape, transcriptional signatures and intracellular signaling cascades in primary tumor cells as well as assessment of comparative serologic response to radiographic assessments of response.

Specimens submitted, by patients who consent to the additional specimen collection, will be processed to maximize their utility for future unspecified research projects and may include, but not limited to, extraction of plasma, serum, DNA and RNA. Specimens will be archived with appropriate safeguards to ensure an efficient system for the prompt linkage and retrieval of the stored samples with the subject's study records.

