5.2 Treatment Grouping and Dosing

Medicare qualifying research related combination chemotherapy:

Stratification will be performed on a 1:1:1 basis to Group A, B or C by willingness to consent to optional biopsies. The first 3 patients will be directly enrolled into cohort C regardless of decision to be included in the optional biopsy portion of the study.

Group A (consented to optional biopsies; 6 patients): umbralisib 800 mg PO daily on Days 1-8; then umbralisib 800 mg oral daily and Ibrutinib 560 mg oral daily

Group B (consented to optional biopsies; 6 patients): Ibrutinib 560 mg PO daily Days 1-8; then umbralisib 800 mg PO daily and Ibrutinib 560 mg PO daily

Group C (deferred consent to optional biopsies or consented to optional biopsies; 12 patients): umbralisib 800 mg PO daily and Ibrutinib 560 mg PO daily

All subjects will receive a maximum of 52 weeks of oral (self-administered) therapy. To provide a means of ensuring oral routes of medication adherence of patients while participating in a clinical trial **Appendix F** "Oral, Sublingual, and/or Buccal Route Medication Adherence Standard Procedure (V 1.0 11-25-2013)" will be followed.

No routine prophylactic antiemetics or pre-medications should be given outside of protocol requirements. However, these medications may be administered for symptoms when they occur, and may be given prophylactically afterwards. Appropriate anti-emetic regimens should be based on the recommendations made by the NCCN guidelines (SOC). http://www.nccn.org/professionals/physician_gls/PDF/antiemesis.pdf

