5.2.1 Guidelines for Administration of umbralisib

- Method of Administration: Umbralisib 4 tablets each 200mg = 800mg will be administered orally once daily.
 Umbralisib should be taken in the morning. (NOTE: After cycle 2 if no CTE have been seen then the patient can have the option to take umbralisib and Ibrutinib dosing together at the same time of day).
- Umbralisib tablets should be swallowed whole with a full glass (approximately 8 ounces) of water. umbralisib tablets should NOT be crushed or chewed.
- Potential Drug Interactions: No Drug Interactions have been reported to date.
- Pre-medications: None

Umbralisib will be self-administered (by the patient). Tablets should be taken at approximately the same time each morning with food. Patients should be instructed to swallow the tablets whole and should not chew or crush them. If a dose of umbralisib is missed, it should be taken as soon as possible on the same day. If a dose is missed, it should not be replaced. If vomiting occurs, no attempt should be made to replace the vomited dose. Study drug compliance should be reviewed with the patient at the beginning of each new treatment cycle. Missed doses should be documented. (Appendix F "Oral, Sublingual, and/or Buccal Route Medication Adherence Standard Procedure (V 1.0 11-25-2013)"

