5.11.5 Peripheral T-cell Characteristics

Ibrutinib and umbralisib have been described to have secondary targets of Itk and CK1ε, respectively [PMID.(22, 23) These molecules play a role in T-helper cell differentiation by promoting or inhibiting Th2 polarization, respectively. We will therefore monitor the change in T- cell characteristics using 10mL of peripheral blood in EDTA from pretreatment and day 8 and 1-month. This will include the interrogation of cytokines (IFN-y, TNF-α, IL-2, IL-4, IL-5, IL-6,

IL10, IL-13), phenotypic markers (CD3, CD4, CD25, CD45RO, CCR6, CCR7, CD27, CD127, CXCR3, HLA-DR, CD38) and intracellular transcription factors (FoxP3, T-bet, GATA3).

6.0 Measurement of Effect:

6.1 Response to therapy:

Response to therapy will be classified as complete response (CR), partial response (PR), stable disease (SD), progressive disease (PD), early death, or not evaluable. Response to therapy will be determined after cycle 2, 4, 6, 9, and 12 (+/- 7 days). After Month 12, efficacy assessments should occur at the investigators discretion.

Patients with a global deterioration of health status requiring permanent discontinuation of study treatment (taken off study) without objective evidence of disease progression will be counted as progressive disease unless a prior CR or PR has been previously documented. Every effort should be made to document the objective progression even after discontinuation of treatment. Deaths will be counted as treatment failure.

Patients will be analyzed with respect to overall survival (OS) and progression-free survival (PFS). Overall survival is defined as time from the first therapy administered on trial until death from any cause. For subjects who are still alive at the time of the study analysis or are lost to follow-up, survival will be censored at the last recorded date that the subject was known to be alive. Progression-free survival is defined as time from therapy until relapse, progression, or death from any cause. Response will be determined by the principal investigator or the co-principal investigators.

CR can be achieved at any response evaluation of umbralisib and ibrutinib.

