Group A: You will take umbralisib 800mg (4 tablets) Day 1-8

Starting day 9, you will take both umbralisib 800mg (4 tablets) and Ibrutinib 560mg (4 capsules) by mouth once a day with a full 8 ounce glass of water until your treating physician tells you to stop. Follow your Medication Calendar that is provided to record your dosing.

Group B: You will take Ibrutinib 560mg (4 capsules) Day 1-8

Starting day 9, you will take both umbralisib 800mg (4 tablets) and Ibrutinib 560 mg (4 capsules) by mouth once a day with a full 8ounce glass of water until your treating physician tells you to stop. Follow your Medication Calendar that is provided to record your dosing.

Group C: You will take both umbralisib 800mg (4 tablets) and Ibrutinib 560 mg (4 capsules) by mouth once a day with a full 8ounce glass of water until your treating physician tells you to stop. Follow your Medication Calendar that is provided to record your dosing.

- Umbralisib should be taken in the AM. (NOTE: After cycle 2 if no side effects have been seen you can have the option to take umbralisib and Ibrutinib dosing together at the same time of day.)
- **Ibrutinib should be taken in the evening. (NOTE:** After cycle 2 if no side effects have been seen you can have the option to take umbralisib and Ibrutinib dosing together at the same time of day.)

Things to know about your medication:

- 1. The dose of the study medications will remain the same during your entire treatment, unless your doctor informs you of a change.
- 2. If your doctor modifies the dose of either medication for any reason, please record the change on your Medication Calendar (Form B).
- 3. You should take your medications at the same time each day with food.
- 4. You should avoid grapefruit and Seville oranges (Known as "Chinese Bitter Orange", bitter orange, sour orange, bigarade orange, or marmalade orange. The Seville orange variety is used in the production of marmalade/cooking) during treatment, as these can alter the absorption of the medications.
- 5. You should swallow the tablets and capsules as a whole, **do not** chew or crush them.
- 6. If you miss a dose of your medications, it should be taken as soon as possible on the same day. If it is missed for the entire day, it should not be made up. If a dose is missed make sure to mark it on your Medication Calendar (Form B).
- 7. If vomiting occurs, no attempt should be made to replace the vomited doses.

Page 58 of 65

Your Doctor is:	Contact Phone #

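### Footnote 9's two-sided three-day windows admit an on-drug baseline blood sample and, in Groups A and B, a day 8 blood sample drawn after the second drug has started

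*Combined protocol and SAP*

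**What the plan says.** **Sampling windows.** Footnote 9 of Section 7.0 gives the mandatory research blood as "pretreatment (day of biopsy or initiation of treatment; (+/- 3 days)), day 8 (+/- 3 days", so each of the first two samples carries its own two-sided allowance. In the schedule table, research blood has no mark under Screening. Its first mark is in the Cycle 1 Day 1 column, whose header also allows three days either way; the Day 8 column header has no allowance.

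**The same samples elsewhere.** Section 5.1 writes "pretreatment (day of biopsy or initiation of treatment), day 8, 1 month (+/- 3 days", with the allowance after the one-month sample only. Sections 5.11.1 and 5.11.3 and Appendix G place it the same way.

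**Dosing.** Section 5.2 gives Group A "umbralisib 800 mg PO daily on Days 1-8; then umbralisib 800 mg oral daily and Ibrutinib 560 mg oral daily" and Group B "Ibrutinib 560 mg PO daily Days 1-8; then umbralisib 800 mg PO daily and Ibrutinib 560 mg PO daily". The patient sheet in Appendix F fixes the changeover for Group A: "Starting day 9, you will take both umbralisib 800mg (4 tablets", together with ibrutinib. Group B has the matching line, and the medication calendars bar the second drug for the first eight days. Section 5.2.1 states "Umbralisib should be taken in the morning"; Section 5.2.2 places ibrutinib in the evening.

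**Biopsies.** Footnote 8 gives the optional core biopsy at Day 0 and the optional aspirate at day 8, without an allowance.

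No section requires the baseline blood to precede the first dose, or the Group A/B day 8 blood to precede the second drug.

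**The concern.** Day 8 is the last day of the single-drug period and the only scheduled time point within it. Blood is the only mandatory sample there, and it is the named source for the T-cell work in Section 5.11.5 and the cell-free DNA work in Section 5.11.3. A Group A or B sample drawn after the second drug starts no longer shows one drug alone, yet it would still count as an in-window day 8 sample.

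Section 5.11.5 gives a reason to keep the two states apart. Of the drugs' secondary targets it says "These molecules play a role in T-helper cell differentiation by promoting or inhibiting Th2 polarization, respectively". A sample on both drugs could therefore combine influences that the lead-in would otherwise show separately.

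The baseline problem is wider. Section 5.11.3 measures cell-free DNA response as a change in allelic fraction, and Section 5.11.5 follows change in T-cell characteristics. A baseline drawn on drug enters every later change for that patient. This can arise in all three groups, including Group C, which starts both drugs on Day 1.

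**Working it through.** The plan states no figure on this point, so there is none to reproduce. The check is a count of calendar dates.

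**Inputs**
- Windows: baseline ± 3 days and day 8 ± 3 days (Section 7.0, footnote 9).
- Second drug starts on Day 9 in Groups A and B (Section 5.2; Appendix F).
- Umbralisib in the morning, ibrutinib in the evening (Sections 5.2.1 and 5.2.2).
- Group sizes 6, 6 and 12, total 24 (Section 5.2).
- The protocol uses a Day 0, so Day 0 is counted as a date.

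**Day 8 window**

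8 − 3 = 5 and 8 + 3 = 11, so Days 5-11, which is 7 dates. Days 5-8 precede the second drug; Days 9, 10 and 11 fall on or after its start.

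- *Group A* adds ibrutinib, taken in the evening. A daytime draw on Day 9 can still precede it. Days 10 and 11 are always on both drugs, so 2 to 3 of 7 dates.
- *Group B* adds umbralisib, taken in the morning. Day 9 counts unless the draw comes before that morning's tablets, so 3 of 7 dates at most.

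**Expected number, if draws were spread evenly over the 7 dates (assumption)**

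- Day 9 in Group A counted as single-drug: 6 × 2/7 + 6 × 3/7 = 1.7 + 2.6 = 4.3 samples.
- Day 9 counted as on both drugs in both groups: 12 × 3/7 = 5.1 samples.

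That is about 4 to 5 of 12.

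**Baseline window**

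| Anchor | Permitted dates | Dates after Day 1 |
|---|---|---|
| Initiation of treatment, Day 1 | Day −2 to Day 4 | Days 2, 3, 4 (3 of 7) |
| Biopsy, Day 0 | Day −3 to Day 3 | Days 2, 3 (2 of 7) |

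Day 1 itself is not required to be pre-dose under either anchor.

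**Interval between the two samples**

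With the Day 1 anchor, the shortest permitted gap is 5 − 4 = 1 day and the longest is 11 − (−2) = 13 days. The nominal gap is 8 − 1 = 7 days.

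**After a one-sided rule**

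Day 8 blood restricted to Days 5-8 has 0 of 4 dates on or after Day 9. Baseline restricted to before the first dose has no date after it.

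**The case against.** The best reply is that the sample is called pretreatment wherever it is described, that Section 5.1 lists it among pre-treatment evaluations, and that four places put the allowance on the one-month sample only. On that view footnote 9 is loosely worded and nobody would draw a baseline on treatment. This has force, and it makes the baseline half an inconsistency to reconcile. It does not close the gap: footnote 9 defines pretreatment by reference to the day of biopsy or initiation and then adds days on both sides. No section says which wording prevails.

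Second, Day 8 already carries an examination and laboratory tests, and consenting patients have the aspirate then. Most bloods would probably be drawn that day. That stands, and it is why the 4 to 5 samples are an upper range.

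Third, Appendix G records the date of each sample and the medication calendar records dosing times, so a late draw could be found and reclassified. That reduces the harm. But reclassifying costs the patient's only scheduled single-drug blood sample, or the true baseline. For a draw on Day 1 itself, a date alone cannot show whether it came before the dose.

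A reader might also infer that the biopsies are affected and that the plan loses its only single-agent readout. The documents do not support this. Footnote 8 fixes the core at Day 0, before treatment, and the aspirate at day 8, with no allowance. The schedule's Day 1 header does span the biopsy row, but it can be read as moving the whole visit. The aspirate remains a second readout in the single-drug period.

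**Conclusion.** Footnote 9 as written admits an on-drug baseline in all 24 patients, and an on-doublet day 8 blood on 2 to 3 of 7 permitted dates in Group A and 3 of 7 in Group B. It conflicts with the sample's own name and with Sections 5.1, 5.11.1 and 5.11.3 and Appendix G. The date counts rest on the stated windows and dosing times; the 4 to 5 of 12 samples rest on the even-spread assumption.

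The consequence is confined to the exploratory T-cell and cell-free DNA readouts. A reader might go further and take this as a threat to the trial's main conclusions, but the primary safety endpoint, response rate and stopping rules do not use these samples. Nor does the plan specify a single-agent or between-group comparison that would be invalidated. That the lead-in serves to show each drug alone is inferred from the design. Section 5.11.5 describes roles of the targets; it does not predict opposing drug effects in these samples. The point is worth correcting because the correction is cheap and a mistimed sample cannot be retaken.

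**What to change.** Make the two blood windows in footnote 9 one-sided, and reconcile it with Sections 5.1, 5.11.1 and 5.11.3, the Day 1 column header of the schedule, and Appendix G:

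- **Baseline blood, all groups:** drawn within three days before the first dose of study drug, and always before that dose.
- **Day 8 blood, Groups A and B:** drawn on Days 5-8, before the first dose of the second drug.
- **Recording:** add the draw time relative to dose to the Appendix G form, beside the date.
- **Late samples:** label them on-treatment or on-doublet, and leave them out of baseline or single-agent comparisons.
- **Biopsy and aspirate:** keep at Day 0 and day 8 as written.

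This changes sampling times only. It adds no visit, sample or change in dosing. The cost is a wording amendment and slightly tighter visit booking: the baseline limit applies to all 24 patients, the day 8 limit to 12.

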8.1 Umbralisib

Classification: Phosphatidylinositol-3-Kinase (PI3K) Delta Inhibitor

Formulation: See Investigator Brochure

Mode of Action: Irreversibly inhibits activity of the Class I Delta isoform of PI3K

How Supplied: umbralisib (micronized): 200 mg tablets

Storage: Store at 25°C. Excursions permitted 15°C to 30°C. Stability: Retest dates will be provided periodically by Sponsor.

Route: Oral

Packaging: umbralisib is provided in HDPE bottles each containing 30 tablets and a silica gel canister

as a desiccant.

Availability: umbralisib is available from TG Therapeutics.

8.2 Ibrutinib

Classification: Irreversible inhibitor of Bruton's Tyrosine Kinase

Formulation: See Investigator Brochure

Mode of action: Irreversibility inhibits activity of Bruton's Tyrosine Kinase

How Supplied: Ibrutinib: 140 mg capsules (hard gelatin capsule). Refer to the ibrutinib Investigator's

Brochure for a list of excipients.

Storage: Store at 20 °C to 25 °C

Route: Oral

Availability: Ibrutinib is available from Janssen Scientific Affairs, LLC.

[figure not shown]
8.3 Administration of Umbralisib and ibrutinib

At each visit, patients will be dispensed sufficient umbralisib and ibrutinib drug supplies until the next visit. Study drug compliance should be reviewed with the patient at the beginning of each new treatment cycle. Missed doses should be documented.

Umbralisib and ibrutinib will be self-administered by the patients. Umbralisib (4 200mg tablets = 800mg) and ibrutinib (4 140mg tablets = 560mg) will be administered orally once daily. Umbralisib should be taken in the morning. Ibrutinib should be taken in the evening. (NOTE: After cycle 2 if no CTE have been seen then the patient can have the option to take umbralisib and Ibrutinib dosing together at the same time of day.)

Umbralisib and ibrutinib tablets should be swallowed whole with a full glass (approximately 8 ounces) of water. Umbralisib tablets should NOT be crushed/opened or chewed. Ibrutinib capsules should not be opened, broken or chewed.

The following adverse events have been reported to occur in patients receiving similar PI3K inhibitors: increased ALT/AST, skin rash, enteritis, and pneumonia.

Refer to the current Investigator Brochure for details of the risks associated with the use of umbralisib, and instructions on how to manage patients.

Prohibitions and restrictions for ibrutinib:

The following guidance should be applied during the perioperative period for subjects who require surgical intervention or an invasive procedure while receiving ibrutinib:

- For any planned surgery or invasive procedure requiring sutures or staples for closure, ibrutinib should be held
 at least 7 days prior to the intervention and should be held at least 7 days after the procedure, and restarted at
 the discretion of the investigator when the surgical site is reasonably healed without serosanguineous drainage
 or the need for drainage tubes.
- For planned minor procedures (such as a central line placement, needle biopsy, thoracentesis, or paracentesis) ibrutinib should be held for at least 3 days prior to the procedure and should not be restarted for at least 3 days after the procedure. For bone marrow biopsies that are performed while the subject is on ibrutinib, it is not necessary to hold ibrutinib for these procedures.
- For emergency procedures, ibrutinib should be held after the procedure until the surgical site is reasonably healed, for at least 7 days after the urgent surgical procedure, or at the discretion of the investigator.

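### Section 8.3's 3-day ibrutinib hold most naturally covers the Day 8 research aspirate, but the Group B and Group C dosing schedules and calendars leave no room for it

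*Combined protocol and SAP*

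**What the plan says.** **The hold.** Section 8.3 introduces its perioperative guidance as applying "for subjects who require surgical intervention or an invasive procedure while receiving ibrutinib". For planned minor procedures, a list of examples that includes needle biopsy, the rule for ibrutinib is: "held for at least 3 days prior to the procedure and should not be restarted for at least 3 days after the procedure". One exemption follows: "For bone marrow biopsies that are performed while the subject is on ibrutinib, it is not necessary to hold ibrutinib for these procedures".

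**The schedule.** Section 5.2 gives Group B "Ibrutinib 560 mg PO daily Days 1-8; then umbralisib 800 mg PO daily and Ibrutinib 560 mg PO daily". The Appendix F patient sheet repeats this: "Group B: You will take Ibrutinib 560mg (4 capsules) Day 1-8". For Day 9 onward the Group A and Group B sheets carry the same instruction: "Starting day 9, you will take both umbralisib 800mg (4 tablets) and Ibrutinib 560mg (4 capsules) by mouth once a day". The Group C sheet reads "Group C: You will take both umbralisib 800mg (4 tablets) and Ibrutinib 560 mg (4 capsules) by mouth once a day", from the start. The Appendix F calendars mark no ibrutinib pause for Group B or Group C.

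**The procedure.** Section 7.0 footnote 8, section 5.11.4 and Appendix G place an image-guided lymph-node FNA on Day 8 for patients who consent to biopsies. The first two list it among the optional biopsies. Appendix G says the sample is for research only and that results do not influence the patient's care.

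**Bleeding precautions tied to the biopsies.** Footnote 8 has anticoagulants held at the investigator's discretion. It does not mention ibrutinib. None of these places refers to section 8.3.

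**The concern.** The FNA date is known before the first dose, so a 3-day pause on either side of it is also known in advance. Yet the dosing documents tell the same patients to take ibrutinib on every one of those days. A site has to break one instruction to keep the other.

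Each choice has a cost. If the calendars are followed, the protocol's own bleeding precaution is set aside for a procedure that brings the patient no benefit. If the hold is followed, Group B has a gap with no study drug that no section mentions. Its Day 8 tissue, which section 5.11.4 uses to measure how treatment alters signalling, is then collected several days after the last dose of the only drug that group has received. If staff differ in what they do, exposure at the sample will vary within a very small group, and no section asks for the time since the last dose to be recorded with the sample.

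**Working it through.** **Inputs**
- Hold: at least 3 days before and after (section 8.3).
- Ibrutinib in the evening: "Ibrutinib should be taken in the evening" (section 8.3). The hour is not given; I assume 18:00, 20:00 or 22:00.
- FNA on Day 8 (section 7.0 footnote 8). The hour is not given; I assume 08:00, 12:00 or 16:00. All nine combinations give the same dose counts.
- Umbralisib starts on Day 9 in Group B and on Day 1 in Group C (section 5.2, Appendix F).
- A cycle is 28 days (section 5.5).

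**1. Does the hold reach the FNA?** The rule covers planned minor procedures, names needle biopsy and exempts one other kind of biopsy. Sections 5.11.4 and 7.0 list the FNA among the biopsies. That favours yes.

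**2. Calendars followed.** Doses before the FNA: Days 1-7 = 7.
- Day 7 dose to FNA: shortest 22:00 to 08:00 = 10 h; longest 18:00 to 16:00 = 22 h.
- FNA to Day 8 dose: shortest 16:00 to 18:00 = 2 h; longest 08:00 to 22:00 = 14 h.
- Pre-procedure hold days achieved: 0 of 3.

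**3. Hold followed, counting at least 72 h each side.**
- A Day 5 dose is too late: its longest interval is Day 5 18:00 to Day 8 16:00 = 70 h.
- The last allowed dose is therefore Day 4. Shortest interval, Day 4 22:00 to Day 8 08:00 = 82 h; longest, Day 4 18:00 to Day 8 16:00 = 94 h. That is 82/24 = 3.4 to 94/24 = 3.9 days.
- A Day 10 restart is too early: its longest interval is Day 8 08:00 to Day 10 22:00 = 62 h.
- The earliest restart is therefore Day 11: its shortest interval is Day 8 16:00 to Day 11 18:00 = 74 h. Counting three full calendar days after the FNA (Days 9, 10 and 11) moves it to Day 12.
- Missed doses = restart day - last dose day - 1: 11 - 4 - 1 = 6, or 12 - 4 - 1 = 7. As a share of cycle 1: 6/28 = 21.4%, or 7/28 = 25.0%.
- Ibrutinib doses before the FNA: 4 instead of 7.

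**4. What each group takes under the hold.**

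| | Days 5-8 | From Day 9 to restart |
|---|---|---|
| Group B | no study drug (4 days) | umbralisib alone, Days 9-10 or 9-11 |
| Group C, biopsied | umbralisib alone | umbralisib alone |
| Group C, not biopsied | both drugs | both drugs |

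**5. Who is affected.** Group B: 6 planned. Group C: only those biopsied, with no number fixed and a ceiling of 12. Biopsies are optional and need an accessible node. Group A takes its first ibrutinib on Day 9 and the Day 0 core is taken before treatment, so neither breaks the wording of the rule.

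**The case against.** The strongest reply is that the text already settles the matter. A hold has meaning only if it interrupts a daily schedule, section 8.3 names needle biopsy, and the patient sheet allows changes that the doctor directs. This largely stands. A reader might infer that the protocol offers two equally good readings; it does not, because the wording favours the hold. What remains is that the calendars omit a pause known in advance and that nothing says what Group B takes on Days 5-8.

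The opposite reply is that the hold does not reach the FNA. Section 8.3 speaks of subjects who require a procedure, and this one is optional. Appendix G names it apart from the core biopsy and describes a fine needle (22 or 25 gauge). This reading is possible but weaker. The section 8.3 list is illustrative, and a narrow reading would give a research-only procedure less protection than a clinical one. The Hemorrhage text in section 8.5 does not help, since it asks for a benefit-risk judgement about surgery.

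A third reply is that neither harm is quantified. That is correct. Section 8.5 reports fatal bleeding, and Grade 3 or higher bleeding in up to 6% of patients, but the documents give no rate for an FNA. On signalling, ibrutinib binds irreversibly. Section 2.2.3 reports at least 90% occupancy for at least 24 hours, which is a minimum, so 82-94 hours off-dose does not establish that inhibition is lost.

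Lastly, the dose loss is confined to cycle 1. Over 12 cycles (12 x 28 = 336 doses) it is 6/336 = 1.8% to 7/336 = 2.1%.

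**Conclusion.** The conflict is real and worth correcting before Day 8 aspirates are taken. It concerns bleeding precautions at the FNA, an undescribed dosing gap in Group B, and the interpretation of exploratory Day 8 tissue. The dose counts rest on evening dosing and a daytime FNA on Day 8 itself.

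Four stronger conclusions are tempting, and the documents do not support them:
- **Day 8 blood is also off-dose.** Not necessarily. Section 7.0 footnote 9 allows 3 days either way, so under the hold blood could be drawn on Day 5, the day after the last evening dose.
- **A planned three-way comparison at Day 8 is lost.** Three regimens are scheduled, but no between-group Day 8 analysis is prespecified. Section 5.11.4 speaks only of change with treatment, and section 10.0 assesses toxicity and efficacy in the whole cohort.
- **18 of 24 patients are affected.** That is a ceiling (6 + 12), and it needs every Group C patient to be biopsied. Group B is the only group that is both defined by biopsy consent and taking ibrutinib before Day 8.
- **The main design is compromised.** The cumulative toxicity and response stopping rules are unaffected.

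**What to change.** Amend section 8.3 and section 7.0 footnote 8 so that one instruction governs the Day 8 FNA, and align section 5.2, the Appendix F sheets and calendars, and Appendix G.

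- **Default:** write the section 8.3 hold into the Group B and biopsied Group C calendars (last dose Day 4, restart Day 11 or 12, with the counting rule stated), and say what Group B takes on Days 5-8.
- **Alternative:** expressly exempt the FNA, as is done for bone marrow biopsy, and state the bleeding precautions that replace the hold.

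Under either option, record the time since the last ibrutinib dose for each Day 8 tissue sample, and analyse tissue taken under the hold as off-dose. The clinical choice is the sponsor's.

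The cost is wording and calendar edits, with no extra patients or procedures. Under the hold, each biopsied Group B or C patient misses 6 or 7 cycle 1 ibrutinib doses, which section 8.3 already implies.
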